PARTNERS HUMAN RESEARCH COMMITTEE PROTOCOL SUMMARY

Answer all questions accurately and completely in order to provide the PHRC with the relevant information to assess the risk-benefit ratio for the study. Do not leave sections blank.

PRINCIPAL/OVERALL INVESTIGATOR

[name]

PROTOCOL TITLE

An online pilot study of Version 2 of the smoking cessation smartphone app "Smiling instead of Smoking" (SiS)

FUNDING

American Cancer Society

VERSION DATE

October 25, 2018

SPECIFIC AIMS

Concisely state the objectives of the study and the hypothesis being tested.

The overall goal of this pilot study is to solicit feedback from nondaily smokers looking for smoking cessation support online (n=270) about Version 2 of a smartphone app we designed to support smoking cessation. Feedback will be collected via passively collected smartphone app usage data, surveys and, in a sub-sample (n=20), online video-conference user feedback sessions. Results will be used to guide the design of Version 3.0 of the "Smiling Instead of Smoking" (SiS) smartphone app. Specifically, our aims are to:

- (1)Assess ease-of-use and helpfulness of the app, as rated by app users 6 weeks after their chosen smoking cessation date
- Test if within-person changes occur in theorized mechanisms of (2) behavior change as nondaily smokers undergo a SiS app assisted quit attempt
- Identify app features in need of improvement, as identified by (3) passively recorded app usage patterns, REDCap open-ended survey items, and, in a sub-sample, user feedback sessions (n=20)

BACKGROUND AND SIGNIFICANCE

Provide a brief paragraph summarizing prior experience important for understanding the proposed study and procedures.

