Briefly describe study design and anticipated enrollment, i.e., number of subjects to be enrolled by researchers study-wide and by Partners researchers. Provide a brief summary of the eligibility criteria (for example, age range, gender, medical condition). Include any local site restrictions, for example, "Enrollment at Partners will be limited to adults although the sponsor's protocol is open to both children and adults."

An estimated 270 participants will participate (i.e., sign consent) in this study based on the following eligibility criteria: (a) 18+ years of age, (b) smartphone ownership (c) current nondaily smoker, who smokes at least weekly, and no more than 25 out of the past 30 days (i.e., 71% of nondaily smokers), (d) has current quit intention (i.e., 65-74% of nondaily smokers), and (e) interested in helping us develop a smartphone app for smoking cessation. We will stop enrollment when n=90 participants have completed the primary endpoint of the study, which is the 6-week follow-up. Our study will be conducted entirely remotely and will require a screening process prior to enrolling participants on the app. Based on our experience in Study 1 (#2017P001106), we expect that 1/3 of participants who initially provide consent will pass the screening process and be retained for the 6-week follow-up. Thus, we are estimating that n=270 will be necessary to sign the initial consent for this study in order for n=90 to complete the primary endpoint of this study.

Briefly describe study procedures. Include any local site restrictions, for example, "Subjects enrolled at Partners will not participate in the pharmacokinetic portion of the study." Describe study endpoints.

Participation will last 6 months, where surveys will be administered prior to the quit day (online, as part of a screening test), and at 2-week, 6-week, 3-month, and 6-month follow-ups of the participant's chosen quit day (Figure 2). Participants will use the

[figure not shown]

Figure 2. Timeline of Your Study Participation

app for a strongly encouraged period of 7 weeks (1 week before, 6 weeks following the quit attempt), and optional continued use thereafter.

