Payment will be by check, where participants will receive a total of five checks, corresponding to the five study interactions at enrollment, 2-week, 6-week, 3-month and 6-month follow-up. Participants are remunerated \$25 for each survey they complete (with the exception of the 6-week survey, for which they will be remunerated \$50), unless they fail to answer 100% of the five randomly placed reading alertness check items correctly (e.g.: "Please answer "not at all confident"."), in which case they receive \$10. (Correctly answering all check items is a screening criterion, which is explained to participants during the screening phone call).

For guidance, refer to the following Partners policies:

Recruitment of Research Subjects

https://partnershealthcare-

public.sharepoint.com/ClinicalResearch/Recruitment Of Research Subjects.pdf

Guidelines for Advertisements for Recruiting Subjects

https://partnershealthcare-

public.sharepoint.com/ClinicalResearch/Guidelines For Advertisements,1.11,pdf

Remuneration for Research Subjects

CONSENT PROCEDURES

Explain in detail how, when, where, and by whom consent is obtained, and the timing of consent (i.e., how long subjects will be given to consider participation). For most studies involving more than minimal risk and all studies involving investigational drugs/devices, a licensed physician investigator must obtain informed consent. When subjects are to be enrolled from among the investigators' own patients, describe how the potential for coercion will be avoided.

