During the phone screen, research staff will provide an overview of the study, and will answer any questions participants may have about the study. If deemed eligible after the phone screen, study staff will send participants a link to the online baseline survey, which contains an electronic consent form. Additionally, study staff will also email a pdf copy of the online consent form to participants, and direct them to the HarvardScholar website that provides this information in written format, so that prospective participants have an opportunity to review the consent form at leisure, prior to encountering it as the first page on the REDCap survey. This is the same process we have used to obtain informed consent for a remote-only longitudinal study on the use of the texting intervention SmokefreeTXT to support smoking cessation in nondaily smokers (protocol #2016P002555). The online consent form will outline the nature of the study, risks and benefits to participation, details on remuneration for participation, and how to contact with PI or IRB staff in case they have any concerns (see attached). Participants must click "I agree to participate in this study" to proceed to the baseline survey.

NOTE: When subjects are unable to give consent due to age (minors) or impaired decision-making capacity, complete the forms for Research Involving Children as Subjects of Research and/or Research Involving Individuals with Impaired Decision-making Capacity, available on the New Submissions page on the PHRC website:

https://partnershealthcare.sharepoint.com/sites/phrmApply/aieipa/irb

For guidance, refer to the following Partners policy:

Informed Consent of Research Subjects:

https://partnershealthcare-

public.sharepoint.com/ClinicalResearch/Informed Consent of Research Subjects.pdf

DATA AND SAFETY MONITORING

Describe the plan for monitoring the data to ensure the safety of subjects. The plan should include a brief description of (1) the safety and/or efficacy data that will be reviewed; (2) the planned frequency of review; and (3) who will be responsible for this review and for determining whether the research should be altered or stopped. Include a brief description of any stopping rules for the study, when appropriate. Depending upon the risk, size and complexity of the

study, the investigator, an expert group, an independent Data and Safety Monitoring Board (DSMB) or others might be assigned primary responsibility for this monitoring activity.

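### Does stopping enrollment at the 90th 6-week completer contradict the estimate of 270 consents?

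*Combined protocol and SAP*

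**What the plan says.** Research Design and Methods sets the stopping rule: "We will stop enrollment when n=90 participants have completed the primary endpoint of the study, which is the 6-week follow-up". The same paragraph gives the expected number of consents: "An estimated 270 participants will participate (i.e., sign consent) in this study". It derives that number from experience in Study 1, where about one third of those who consented passed screening and stayed to 6 weeks: "we are estimating that n=270 will be necessary to sign the initial consent for this study in order for n=90 to complete". Specific Aims repeats the figure without the word estimated, describing the goal as to "solicit feedback from nondaily smokers looking for smoking cessation support online (n=270").

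Four statements fix the time between consent and the endpoint:

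- Consent Procedures places consent at the start of the baseline survey: staff send "a link to the online baseline survey, which contains an electronic consent form".
- Research Design and Methods puts that survey before the quit day: "surveys will be administered prior to the quit day (online, as part of a screening test").
- The 6-week survey is counted from the quit day.
- Participants use the "app for a strongly encouraged period of 7 weeks (1 week before, 6 weeks following the quit attempt").

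The protocol states no accrual rate, recruitment period, pause in intake or maximum number of consents. The sample-size paragraph says that the study is not sized to detect an effect.

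**The concern.** The rule and the forecast refer to different moments. The 270 is the number of consents that should eventually produce 90 completers. The rule keeps enrollment open until the 90th completion has been seen, and that person consented at least 6 and about 7 weeks before. Anyone who consents in between is extra. For any positive accrual rate, therefore, the expected number of consents exceeds 270, and the expected number of completers exceeds 90.

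The figure stands where the review committee asks for anticipated enrollment, and payments are made per participant. The protocol also does not say in so many words what happens to people who are mid-follow-up when the 90th participant completes. That might raise doubt about who enters the Week 6 summaries and the repeated-measures models.

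**Working it through.** **Inputs from the protocol.** Target of 90 six-week completers. Yield from consent to completion of 1/3. Lag L of at least 6 weeks (quit day to endpoint), about 7 with the week of app use before the quit day. Payments from Table 1 in Recruitment Procedures.

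**Assumption.** The accrual rate r is not given. I take r = 270/T, where T is the number of weeks needed for the first 270 consents, with steady intake and no pause.

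**The plan's own figure.** 90 / (1/3) = 270. It reproduces exactly.

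**Expected total under the rule.** Completers seen by week t number (1/3) × r × (t − L). Setting this to 90 gives r × t = 270 + L × r consents. The L × r late consents yield L × r / 3 further completers.

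| Assumed T (weeks) | r per week | 7r | Consents / completers, L = 7 | Excess over 270 | Consents / completers, L = 6 |
|---|---|---|---|---|---|
| 104 | 2.60 | 18.2 | 288 / 96 | 7% | 286 / 95 |
| 52 | 5.19 | 36.3 | 306 / 102 | 13% | 301 / 100 |
| 26 | 10.38 | 72.7 | 343 / 114 | 27% | 332 / 111 |
| 13 | 20.77 | 145.4 | 415 / 138 | 54% | 395 / 132 |

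**Chance of staying at or below 270.** In simulation with random arrivals and L = 7, this is about 23%, 6%, 0.1% and 0% for T = 104, 52, 26 and 13. These figures need a comparator. With no lag at all, the chance that 270 consents give at least 90 completers (binomial, p = 1/3) is 52%, so 270 would be exceeded about 48% of the time anyway.

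**Comparison with the uncertainty already in the estimate.** The standard deviation of the number of consents needed for 90 completers is √(90 × 2/3) / (1/3) = 23. The shift at T = 104 (18) is below one standard deviation. An error in the yield has the same effect as the lag: 90/288 = 31.3% and 90/306 = 29.4%, against the assumed 33.3%. At faster accrual the lag dominates: 90/343 = 26.2% and 90/415 = 21.7%.

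**Payments.** A full participant without a Skype session receives up to 20 + 25 + 25 + 50 + 25 + 25 = $170. The extra completers number 7r/3 = 6.06, 12.12, 24.23 and 48.46, which gives up to about $1,030, $2,060, $4,119 and $8,238. Enrollment payments to extra people who do not go on would be added. The protocol states no total budget against which to set these sums.

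**People in follow-up at the stop.** The rule stops enrollment, not follow-up. Research Design and Methods has participation last 6 months. Under Recruitment Procedures, "participants will receive a total of five checks, corresponding to the five study interactions", the last at 6 months. The Aim 2 model uses all five time points. Read together, these passages mean that people already enrolled continue and are analysed.

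**The case for a change.** The best case for a change is that the omission runs in one direction. Calling 270 an estimate covers random error, but not a lag that can be foreseen from the protocol's own timeline. Specific Aims drops the qualifier. Reading enrollment as enrollment on the app does not help, because consenting must continue for as long as the app stays open to new users. With L = 7, the excess stays within 3% (about 8 people) only if accrual is at most 8.1/7 = 1.16 consents per week, or some 233 weeks to reach 270.

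Much of this stands: without a pause, the expected total is above 270, and by a wide margin if recruitment is fast. Three points limit it. First, steady intake is itself an assumption. Entry runs through a phone screen and a link sent by staff, the investigators review recruitment weekly, and the sex balance and the 54% ceiling on non-Hispanic White participants may slow late intake. Second, the bare figure in Specific Aims is a short form of the one that Research Design and Methods qualifies twice. Third, the remedies gain little. Closing consent on projected completers gives up an observed trigger that guarantees 90 for one that may fall short. Restating the forecast needs an accrual rate that the protocol does not contain.

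**Conclusion.** No change to the plan follows. The arithmetic behind 270 is correct for what it claims, the consents expected to yield 90 completers. It is a planning forecast, and the stopping rule is what governs. Followed as written, the rule delivers at least 90 six-week completers. The likely cost is some extra participants in a study described as minimal risk: on assumed recruitment periods of 104 down to 13 weeks and a 7-week lag, about 18 to 145 more consents and 6 to 48 more completers. The size rests wholly on the accrual rate, which cannot be taken from the documents.

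No estimate, error rate or conclusion depends on the difference. Aims 1 and 3 are descriptive, Aim 2 is exploratory, and additional completers make all three slightly more precise. Running past the forecast is a fair price for a rule that secures the target. A remark that consents may exceed 270 would do no harm, but the analysis does not need it.

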Participants will complete two types of assessment: (1) surveys, and (2) (in a sub-sample) user feedback sessions conducted via Skype. Potential participants will click-through to the study website. This website will explain that participants must call study staff in order to be phone-screened and to participate in the study. During the phone-screen, participants will be directed to complete an online survey via REDCap. Within the survey, participants will be asked if they would be willing to participate in an online video-conference user feedback session after they have used the app for seven weeks (1 week pre, 6 weeks post their chosen smoking quit day). Participation in the user feedback session is optional. Participants will receive survey links for 2-week, 6-week, 3-month and 6-month follow-ups via an emailed link. If selected for the online user feedback sessions (selected at random from interested participants), participants will receive an email and/or phone call upon completing their 6-week survey to set up the user feedback session.

The online user feedback sessions (n=20) will consist of the participants, and 1-2 members of the study staff. Relatively little guidance will be provided in this setting. Instead, 4 open-ended questions will be posed (i.e., did the app help you in your quit attempt? What did you like? What did you dislike? How could the app be improved?). All conference calls will be video-recorded for later analysis.

Sample size and Power Considerations: The primary goal of this study is to gather qualitative input rather than data to detect a pre-specified effect. The goal of this pilot study is to get input from app users who are interacting with the app and study staff completely remotely, without the benefit of inperson interaction, which is closer to the real-world experience potential users would have than the participants in Study 1. Thus, to identify issues not identified within the smaller sample in Study 1, we tripled the sample size of the current study, Study 2.

Planned Analyses:

Partners Human Subjects Research Application Form Version Date: October 15, 2014

Aim 1 (Ease-of-use and usefulness). To assess the degree to which SiS Version 2 is easy to use and perceived as useful by nondaily smokers attempting to quit smoking, we will use the Week 6 survey data, and will calculate means and standard deviations for the survey items querying ease of use and usefulness for each feature of the app.

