Aim 2 (Within-person changes). To test if nondaily smokers utilizing SiS Version 2 experienced changes over time on constructs theorized to underlie smoking cessation, we will use the online survey data and fit one repeated measures mixed effects model per construct of interest (i.e., desire to smoke, mood, self-efficacy to quit/stay quit, motivation), where the construct will be the dependent variable, and time (0=baseline, 1=2-week, 2=6-week, 3=3-month, 4=6-month) will be the predictor. Correlations over time will be modeled with an unstructured covariance matrix. A contrast statement will be used to compare baseline versus follow-up. Given the explorative nature of this study, we will not correct for multiple testing.

Aim 3 (Identify app features in need of improvement). To identify features of the app that are in need of improvement, we will examine the passively generated app usage data as nondaily smokers enrolled in our study undergo their quit attempts, and will generate descriptive summary statistics on these usage data. To gain deeper insight, we will also conduct user feedback sessions with a randomly selected subsample of participants.

For studies involving treatment or diagnosis, provide information about standard of care at Partners (e.g., BWH, MGH) and indicate how the study procedures differ from standard care. Provide information on available alternative treatments, procedures, or methods of diagnosis.

Not applicable.

Describe how risks to subjects are minimized, for example, by using procedures which are consistent with sound research design and which do not unnecessarily expose subjects to risk or by using procedures already being performed on the subject for diagnostic or treatment purposes.

Risks are expected to be minimal, and include breach of confidentiality, subject discomfort form answering questions about smoking, and discomfort from quitting smoking (see below). We will minimize these risks by safeguarding electronic data capture by using HIPAA-compliant electronic data capture processes, assuring participants that they do not need to answer any questions they do not want to answer, and by providing information on how to manage smoking cessation.

Describe explicitly the methods for ensuring the safety of subjects. Provide objective criteria for removing a subject from the study, for example, objective criteria for worsening disease/lack of

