improvement and/or unacceptable adverse events. The inclusion of objective drop criteria is especially important in studies designed with placebo control groups.

A subject will be removed from the study if he or she no longer wishes to participate for any reason. A subject may also be removed from the study by the PI, if he or she cannot comply with study procedures (e.g., responds incorrectly to survey check items, cannot install the app on his/her smartphone) or causes undue distress to study staff (e.g., becomes belligerent towards study staff).

FORESEEABLE RISKS AND DISCOMFORTS

Provide a brief description of any foreseeable risks and discomforts to subjects. Include those related to drugs/devices/procedures being studied and/or administered/performed solely for research purposes. In addition, include psychosocial risks, and risks related to privacy and confidentiality. When applicable, describe risks to a developing fetus or nursing infant.

Potential Risks: Participation will last 6 months, where surveys will be administered at enrollment, 2-week, 6-week, 3-month, and 6-month follow-up. Participants will use the app for a strongly encouraged period of 7 weeks (1 week before, 6 weeks following the quit attempt), and optional continued use thereafter. Additional tasks are potential participation in online video-conference user feedback sessions, as summarized in Figure 2. As such, the potential risks in the study are considered minimal and include (1) potential discomfort related to completing questionnaires about potentially sensitive information such as smoking, (2) potential breach of confidentiality and/or privacy, and (3) potential discomfort in quitting smoking (i.e., withdrawal symptoms, craving, etc.).

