Protection Against Risks: For the possibility of subjective discomfort from answering questions, any distress will be minimized by assuring participants that they can refuse to answer any question that they do not feel comfortable addressing and that they may withdraw from the study at any time without penalty. To protect against breach of confidentiality, we will assign a numeric study ID to each participant, which will be the primary identifier by which this person's progress through the trial will be reviewed. The database linking names and study identification numbers will be kept in a separate password protected file. Only study staff will have access to this database. All staff are or will be fully trained in relevant ethical principles and procedures, including confidentiality. All assessment and treatment procedures will be closely supervised by the PI. Most of the data will be captured electronically. For surveys and data entry by study staff, we will be using Partners implementation of REDCap (Research Electronic Data Capture) https://redcap.partners.org, which is a secure, web-based application designed to support data capture for research studies, and which is fully compliant with HIPAA-Security guidelines. The data generated by using our custom-built app (i.e., app usage data) will be kept on secure

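### Does Aim 1 need a written rule for Week 6 ratings of app features that a respondent never used?

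*Combined protocol and SAP*

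**What the plan says.** The Aim 1 paragraph under Planned Analyses names the Week 6 survey as its data source and says the team "will calculate means and standard deviations for the survey items querying ease of use and usefulness for each feature of the app". Specific Aims describes these ratings "as rated by app users 6 weeks after their chosen smoking cessation date".

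Usage data belong to Aim 3. There the team will examine the passively recorded data and "will generate descriptive summary statistics on these usage data". Specific Aims adds open-ended survey items and 20 user feedback sessions as further sources for deciding what to improve.

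Four other places bear on who might rate what:

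- Research Design and Methods has participants using the "app for a strongly encouraged period of 7 weeks". It sets no minimum amount of use.
- The text on minimizing risks speaks of "assuring participants that they do not need to answer any questions they do not want to answer".
- The removal criteria cover a participant who "cannot comply with study procedures (e.g., responds incorrectly to survey check items, cannot install the app on his/her smartphone", among others.
- Under remuneration, full survey pay is given "unless they fail to answer 100% of the five randomly placed reading alertness check items correctly".

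Protection Against Risks says "we will assign a numeric study ID to each participant", so ratings and usage could be linked for each person if wanted. No section says they will be. The survey items themselves are not in the document.

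**The concern.** An app user has not necessarily used every feature, yet the unit of the Aim 1 analysis is the single feature. Use is encouraged without a floor, survey pay depends on completion and check items, and non-use is not among the listed examples for removal. A participant could therefore reach Week 6 having never opened a given feature and still be asked to rate it.

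Two things could then happen. If such people answer, the feature's mean blends experience with guesswork. If they skip the item, the mean rests on a smaller, self-selected group, and the plan does not promise to report its size. A little-found but well-liked feature and a widely used but mediocre one could end up with the same mean, although they call for different design responses. Because the results are meant to shape Version 3, a reader would want to tell these cases apart.

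**Working it through.** **The plan's own figure.** Enrollment stops at 90 completers of the 6-week follow-up, and one third of those who consent are expected to get that far: 90 / (1/3) = 270, as stated. The 90 is the number of Week 6 completers. It caps the number of raters of any feature but does not fix it.

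**What is and is not specified for Aim 1.**

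| Element | Stated? |
|---|---|
| Raters | Yes: app users at Week 6 |
| Data source | Yes: Week 6 survey |
| Items | Yes: ease of use and usefulness, per feature |
| Statistic | Yes: mean and SD |
| Handling of never-used features | No |
| n per feature | No |
| Link to usage log | No |

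The first four rows are enough to compute the result. Read plainly, it is the mean over respondents who answered the item.

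**How far a mean could move if non-users answer.** The documents supply none of the inputs, so all are assumed: a 1-5 item, users' mean 4.2, share using the feature u, non-users' mean m.

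Reported mean = u × 4.2 + (1 − u) × m

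Shift = (1 − u) × (m − 4.2)

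| m | u = 0.8 | u = 0.4 | u = 0.2 |
|---|---|---|---|
| 5 | +0.16 | +0.48 | +0.64 |
| 4 | −0.04 | −0.12 | −0.16 |
| 3 | −0.24 | −0.72 | −0.96 |
| 2 | −0.44 | −1.32 | −1.76 |

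For example, at u = 0.2 and m = 5 the shift is 0.8 × 0.8 = +0.64; at m = 2 it is 0.8 × (−2.2) = −1.76. The sign depends wholly on whether non-users rate above or below users, on which the documents are silent. If the questionnaire has a did-not-use answer or skip logic, every entry is zero.

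**Precision if non-users skip.** Here n = 90u, and with an assumed SD of 1 the 95% half-width is t(0.975, n − 1) / √n.

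| Share using | n | Half-width |
|---|---|---|
| 100% | 90 | 0.209 |
| 80% | 72 | 0.235 |
| 40% | 36 | 0.338 |
| 20% | 18 | 0.497 |

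Reporting n beside each mean, as any table of means and SDs normally does, makes this loss visible.

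**Where a design decision would come from.** Aim 1 plans no ranking, threshold, test or comparison across features. Choosing what to improve is Aim 3, which draws on usage, open-ended comments and feedback sessions. A rarely opened feature could surface there if the log is kept by feature, which Aim 3 implies but does not state.

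**The case for a change.** The best argument for a change is that a descriptive mean still needs a defined population, and that adding one costs two or three sentences and a merge by study ID. Aggregate usage figures under Aim 3 do not show whether the people who rated a feature had used it; only a link at participant level does. Even if the survey offers a did-not-use answer, the plan does not say how it enters the mean.

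Part of this stands. The three omissions are confirmed, no other section fills them, and a split of ratings by logged use would be more informative than the overall mean alone.

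It does not show that the plan goes wrong as written. Perceived usefulness among all Week 6 respondents is a legitimate quantity in its own right, and a users-only mean is another choice with its own defects: fewer raters, a group that selected itself, and a cut-off for use that someone must pick. Skip logic and did-not-use options belong in the questionnaire, so their absence from a brief protocol summary says little about whether they exist.

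The evidence that non-users will rate features is also thin. The removal criteria list examples only, the pay rule says nothing on feature use, and the right to skip questions is offered to limit discomfort.

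**Conclusion.** No change to the plan is needed. This is missing detail that an analyst fills sensibly when the tables are made: show n with each mean and SD, count a did-not-use answer as no rating, and, if the log is by feature, set the ratings beside logged use among the same Week 6 respondents. None of that needs to be fixed in advance for a descriptive aim in a pilot whose stated main purpose is qualitative input.

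The size is unknown. It is zero if the survey screens out non-users. Otherwise, under the assumptions above, it lies between −1.76 and +0.64 points, with both extremes requiring that four in five respondents never used the feature. No inference, sample size or error rate is touched.

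This conclusion rests on two readings: that the Aim 1 means are taken over Week 6 respondents who answered the item, and that decisions about features are made under Aim 3 and not from the means alone. If the Version 3 design were to rest on ranking features by their Aim 1 means, the point would carry more weight, but the plan does not propose that.
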